The effect of caudal anesthesia block on perioperative pain control and reduction of the anesthetic agent in pediatric infra-umbilical surgery: A prospective randomized trial study

(IRB approval number: 123311219, Date 05/01/2020

Abstract

Background: Caudal epidural block (CEB) is a commonly performed neuraxial block to provide effective pain relief and analgesia in pediatric patients undergoing infra-umbilical surgery.

Aims: This study aimed to compare the effectiveness of adding CEB to general anesthesia (GA) in terms of intra- and post-operative pain management.

Design: Prospective, randomized case-controlled study.

Setting: Operation theater, and postoperative recovery rooms at Salmaniya medical complex, Bahrain.

Material and methods: A total of 74 patients aged two months to six years with American Society of Anesthesiology physical status classification (ASA PS) I were recruited over a six-month period between December 2019 and May 2020. Patients were allocated into two groups (with CEB, (group A) or without CEB (group B)). Both groups were compared based on hemodynamic stability, level of sedation, analgesia need, pain score, and parental satisfaction. Postoperative pain was evaluated by the Children's Hospital Eastern Ontario Pain Scale (CHEOPS), Faces Pain Scale-Revised (FPS-R), and Face, Legs, Activity, Cry CONSOL ability (FLACC) scales.

Statistical analysis: Data were analyzed using SPSS program. Categorical and numerical variables of both groups were compared.

Results: Patients with CEB had better hemodynamic stability during the surgical procedure based on heart rate ($P=0.039$). Pain intensity scores were less in patients with CEB than those without

($P<0.001$). Fentanyl consumption was lower in group A compared to group B at the end of surgery ($P=0.002$). They were also ambulated earlier and discharged sooner than those without CEB. Parental satisfaction was 92.1% in group A compared to 63.9% in group B ($P=0.012$).

Conclusions: Adding CEB to GA for intraoperative and perioperative pain control in pediatric patients undergoing infra-umbilical surgery makes it more effective, safer, and with better parental satisfaction. .

Keywords: Caudal anesthesia, general anesthesia, perioperative, sedation, analgesic, pain management, pediatric.

Key messages:

- Using general anesthesia (GA) alone for intraoperative and perioperative pain control in pediatric patients undergoing infra-umbilical surgery requires high doses of opioids and inhalation agents and increases postoperative analgesic use leading to prolonged recovery.

Caudal epidural block (CEB) has faster start of sensory and motor block, and longer

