### **Study population**

The Consolidated Standards of Reporting Trials (CONSORT) checklist was used for the enrolment and allocation of patients. Children aged between two months and six years who were undergoing infra-umbilical surgeries with ASA PS I were randomly allocated to either group A (GA with CEB) or to group B (GA without CEB)., Both groups were compared based on hemodynamic stability, level of sedation, analgesia need, pain score, and parental satisfaction. Postoperative pain was evaluated by the Children's Hospital Eastern Ontario Pain Scale (CHEOPS), Faces Pain Scale-Revised (FPS-R), and Face, Legs, Activity, Cry CONSOL ability (FLACC) scales

The raw data which was collected from case report forms were entered into a Microsoft Excel Spreadsheet initially. Then, the data have been transferred to and analyzed by IBM SPSS Statistics software version 21. The categorical and numerical variables of both groups were analyzed and compared. Data are expressed as  $n$  (%), mean  $\pm$  standard deviation or median and interquartile range (IQR) according to distribution normality. Continuous variables were compared using the Mann-Whitney U test, and categorical variables were compared using Fisher's exact test or Pearson Chi-square test.  $P < 0.05$  was considered statistically significant. The confidence interval was set at 95%.

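### Parental satisfaction, one of the abstract's conclusions, is reported with figures that disagree between the abstract and Table 2 and do not fit Table 2's own denominators

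*Protocol*

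**What the plan says.** **Satisfaction in the abstract.** The Results paragraph of the Protocol abstract states: "Parental satisfaction was 92.1% in group A compared to 63.9% in group B", with P=0.012. The Conclusions paragraph says that adding the caudal block "makes it more effective, safer, and with better parental satisfaction".

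**Satisfaction in the SAP.** The Study population section lists parental satisfaction among the outcomes compared and says that "categorical variables were compared using Fisher's exact test or Pearson Chi-square test". The available text does not define the satisfaction levels or say which of them count as satisfied. Table 2 prints:

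| Level | Group A | Group B | P |
|---|---|---|---|
| Good | 30 (80%) | 5 (20%) | <0.002 |
| Perfect | 30 (80%) | 5 (20%) | <0.001 |

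**Numbers of children.** The abstract's Material and methods paragraph reports recruiting "A total of 74 patients aged two months to six years" and then says "Patients were allocated into two groups", without arm sizes. The SAP says that the CONSORT "checklist was used for the enrolment and allocation of patients". Tables 1 and 2 are both headed n=36 for group A and n=36 for group B.

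**The concern.** A reader who wants to know how much the block improved parental satisfaction finds two accounts. The percentages in the abstract appear nowhere in Table 2. In Table 2 the count and the percentage in the same cell do not agree under the printed column size, and two different levels carry identical entries. Because satisfaction is named in the conclusions, the reported size of a headline result is at stake.

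The difference between 74 recruited and 72 tabulated adds a smaller question: whether the abstract and the tables describe the same set of children.

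**Working it through.** **Inputs.** Abstract: 74 recruited; 92.1%, 63.9%, P=0.012. Tables 1 and 2: n=36 per group, and the counts and percentages printed there.

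**1. Does n=36 fit the rows beside satisfaction?** Postoperative analgesia: 3/36 = 8.3%, 33/36 = 91.7%, 36/36 = 100%, all as printed. The sex counts in Table 1 also sum correctly: 16 + 20 = 36 and 15 + 21 = 36. The header is therefore consistent with the neighbouring counts.

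**2. Table 2 satisfaction on n=36.** Group A: 30/36 = 83.3%, printed 80%. Group B: 5/36 = 13.9%, printed 20%. Neither is reproduced.

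**3. Other denominators.**
- Group A: 30/0.80 = 37.5, not a whole number. The neighbours are 30/37 = 81.1% and 30/38 = 78.9%, so no whole denominator rounds to 80%.
- Group B: 5/0.20 = 25, which is not 36.
- Percentages across the row: 30/35 = 85.7% and 5/35 = 14.3%. These do not fit either.

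**4. The two levels together.** If Good and Perfect are exclusive and both rows are as the authors intended, group A has 30 + 30 = 60 children out of 36, which is impossible, and group B has 5 + 5 = 10, or 10/36 = 27.8%. Both statements fail if the repeated row is an extraction fault.

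**5. Size of the difference.**
- Abstract: 92.1 − 63.9 = 28.2 points.
- One Table 2 row, printed percentages: 80 − 20 = 60 points.
- One Table 2 row, counts over 36: (30 − 5)/36 = 69.4 points.

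**6. P values.** For 30/36 against 5/36, Fisher's exact test gives about 3.5 × 10⁻⁹. Both printed bounds are then true, but identical counts should carry one P value, so the two bounds are a further sign that a row may be misprinted. The abstract's 0.012 satisfies neither bound.

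**7. Secondary query on numbers.** 36 + 36 = 72, and 74 − 72 = 2 children (2/74 = 2.7%). Assume that the abstract's percentages are proportions of children. With n=36, 92.1% is then unattainable: 33/36 = 91.7% and 34/36 = 94.4%. Fractions with n up to 74 that round to 92.1% are 35/38 and 58/63; those that round to 63.9% are 23/36, 39/61 and 46/72. The only pair totalling 74 or fewer is 35/38 with 23/36, and 38 + 36 = 74. As a 2×2 table, that pair gives Fisher P = 0.0043 and Pearson P = 0.0032 (0.0077 with Yates correction), not 0.012. If the satisfied children are split into two levels, 38 of 862 possible splits give a Pearson P that rounds to 0.012. The P value therefore neither confirms nor excludes 38 + 36.

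**8. Table 1 sex percentages.** On n=36 the values are 44.4% and 55.6% in group A (printed 13% and 15%) and 41.7% and 58.3% in group B (printed 11.25% and 15.75%). Three of the four printed values equal the count times 0.75 (20, 15 and 21 give 15, 11.25 and 15.75). This looks clerical, and no conclusion depends on it.

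**The case against.** The strongest reply has four parts.

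**Recruited is not analysed.** More children recruited than analysed is ordinary. The abstract does not say that all 74 were allocated, part of the SAP text and the figures are not available here, and the SAP refers to CONSORT. This stands, and it is why the head count is only a query. A reader might infer that two randomised children were dropped; the documents do not show that.

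**The table may be damaged.** The satisfaction rows follow a gap, have an extra column and no header of their own, and sit under a caption that covers only CHEOPS pain scores. That n=36 applies to them is inferred from the header above and from the analgesia rows. A repeated row or a misread digit is possible; for illustration, 20 and 5 out of 25 would give exactly 80% and 20%. This stands as a caution. A reader might infer that at least 13 group B children (23 − 10) were counted as satisfied at a level not shown. That needs both rows to be correct as printed, and it fails if one is a duplicate.

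**The outcomes may differ.** The abstract may combine levels, while Table 2 shows them singly. That could explain a difference between the two places. It could not explain the mismatch of count and percentage within Table 2, and without a definition the reader cannot tell.

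**The 38 + 36 reading is a reconstruction.** It rests on an unseen scoring rule and does not give P=0.012 as a 2×2 table. A reader might infer that the abstract and the tables use different analysis sets, with both missing children in group A. The percentages hint at this and no more.

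**Conclusion.** The point holds as a reporting inconsistency. Satisfaction is 92.1% against 63.9% in the abstract and 30 (80%) against 5 (20%) in each of two Table 2 rows. The Table 2 entries fit neither 36 per group nor each other. The apparent difference ranges from 28.2 to 69.4 points, with the reservation that these may not be the same quantity. Confidence in the printed mismatch is high, subject to the table having been read correctly.

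The direction favours group A in each reading, so the documents do not support saying that the satisfaction conclusion is reversed. Nor do they support calling P=0.012 wrong, since a test over more than two levels could give it.

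The 74 against 72 is a question to answer, not a shown error. Confidence that the abstract and tables use different analysis sets is low. The analgesia result does not depend on it: giving the two children the least favourable outcomes still leaves at least 36/38 − 3/36 = 86.4 points between the groups.

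**What to change.** 1. Check the satisfaction data against the case report forms.
2. Define the outcome once: its levels, whether they are exclusive, and which count as satisfied.
3. Correct the counts, percentages and P value on one stated denominator, so that the abstract and Table 2 agree, and name the test used.
4. Confirm the numbers recruited, randomised and analysed in each arm, with the reason for any exclusion. If randomised children with outcome data were left out, include them in the arm to which they were randomised.
5. Correct the Table 1 sex percentages at the same time.

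The cost is a check of source records and a re-run of two small tables. In Table 2's satisfaction rows, counts, percentages or denominators must change. The abstract's satisfaction figures, or the 74, may change too. No further sensitivity analysis of analgesia is needed.

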## Tables and Figure legends

**Table 1.** Demographic parameters of children with (group A) or without (group B) caudal block anesthesia.

[figure not shown]
Demographic parameters	Group A (n=36)	Group B (n=36)	P
Age (months), mean $\pm$ SD	20.68 $\pm$ 1.7	29,688 $\pm$ 3.4	0.3
Sex			
Female	16 (13%)	15 (11.25%)	0.5
Male	20 (15%)	21(15.75%)	
Heights (cm), mean $\pm$ SD	90 $\pm$ 2.08	103 $\pm$ 4,2	0.8
Weights (kg), mean $\pm$ SD	9 $\pm$ 1,05	12 $\pm$ 3,02	0.6

SD= standard deviation.

[figure not shown]
**Table 2.** Differences between children with or without caudal block anesthesia in the average pain scores at the various time points according to Children's Hospital Eastern Ontario Pain Scale (CHEOPS).

Variables	Group A (n=36)	Group B (n=36)	P
CHEOPS Score average	3 $\pm$ 0.11	5 $\pm$ 0.49	<0.005
At 30 minutes	2.6 $\pm$ 0.41	4 $\pm$ 0.44	<0.003
At 1 hour	2.11 $\pm$ 0.98	4 $\pm$ 0.54	<0.0001
At 2 hours	3 $\pm$ 0.44	4 $\pm$ 0.65	<0.003
At 6 hours	3.05 $\pm$ 1.53	4.80 $\pm$ 2.04	0.005

Postoperative analgesia	Yes	3.0 (8.3%)	36 (100%)	<0.001
	No	33 (91.7%)	0.0 (0.0%)	
Parental satisfaction	Good	30 (80%)	5.0 (20%)	<0.002
	Perfect	30 (80%)	5.0 (20%)	<0.001

**Figure 1.** Effect of caudal block versus non-caudal block anesthesia on pain intensity at 1 and 6 hours and the degree of sedation in children undergoing infra-umbilical surgery under general anesthesia.

**Figure 2.** Effect of caudal block versus non-caudal block anesthesia on movement score at 1 and 6 hours postoperatively in children undergoing infra-umbilical surgery under general anesthesia.

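### The headline pain result (P<0.001) names no scale or time point, and the only tabulated scale prints a 6-hour P of 0.005 that fits neither the abstract nor its own row.

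*Protocol*

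**What the plan says.** The protocol abstract (Material and methods) enrols children "aged two months to six years" and lists the pain instruments: "Postoperative pain was evaluated by the Children's Hospital Eastern Ontario Pain Scale (CHEOPS), Faces Pain Scale-Revised (FPS-R"), with FLACC as the third. The SAP (Study population) repeats the list for the same population: "Children aged between two months and six years who were undergoing infra-umbilical surgeries with ASA PS I were randomly allocated". The text available gives no main scale, no main time point and no rule for which child is scored on which scale. The SAP assigns continuous variables to the Mann-Whitney U test at the 0.05 level.

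The abstract's Results give one pain finding, "Pain intensity scores were less in patients with CEB than those without", followed by P<0.001. No scale, time, group value or confidence interval is attached.

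SAP Table 2 reports CHEOPS only. Its last time point reads "At 6 hours 3.05 $\pm$ 1.53 4.80 $\pm$ 2.04 0.005". The other rows carry P-values of <0.005 (average), <0.003 (30 minutes), <0.0001 (1 hour) and <0.003 (2 hours). Table 2 does not say whether ± is a standard deviation or a standard error. The Figure 1 legend refers to pain intensity at 1 and 6 hours without naming a scale, and the figure is not shown.

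**The concern.** Pain control is the stated aim, so this sentence is the main result. With three scales and several time points, a single P-value with no referent cannot be checked, and a reader will take it to describe postoperative pain in general. The one place where it can be compared with data, the 6-hour CHEOPS row, prints a P five times the abstract's upper bound. If that row's P is also wrong for its own means and spreads, then the abstract, the table's P and the table's summary values disagree three ways, and none of them can be cited safely.

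**Working it through.** **Inputs.** Means, spreads and P-values come from SAP Table 2, with n = 36 per arm from its header. Ages come from SAP Table 1.

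**Step 1: abstract against table.** The printed 6-hour P is 0.005, and 0.005 / 0.001 = 5, so it does not meet the abstract's bound. The 1-hour entry (<0.0001) does meet it. The entries <0.005 and <0.003 are upper bounds and are compatible with it.

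**Step 2: try to reproduce the printed 6-hour P.** Difference = 4.80 − 3.05 = 1.75.

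- ± as standard deviation: standard error of the difference = √((1.53² + 2.04²)/36) = √(6.5025/36) = 2.55/6 = 0.425. t = 1.75/0.425 = 4.12 on 70 degrees of freedom, two-sided P = 0.00010 (Welch 0.00011). The least favourable rounding of the printed values gives 0.00012.
- ± as standard error: standard error of the difference = √(1.53² + 2.04²) = 2.55. z = 1.75/2.55 = 0.69, P = 0.49.

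Neither reading gives 0.005. With ± as standard deviation, P = 0.005 would need about 19 children per arm.

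**Step 3: does the arm size matter?** The abstract states "A total of 74 patients", while the tables have 36 + 36 = 72. The abstract's satisfaction rates fit 35/38 = 92.1% and 23/36 = 63.9%, and 38 + 36 = 74. Using 38/36 or 37/37 gives a 6-hour P of about 0.00008, so the arm sizes need reconciling but do not explain the discrepancy.

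**Step 4: does the planned test matter?** For each of five distribution shapes (normal, uniform, gamma, exponential, lognormal), 3000 data sets were simulated with exactly the printed means and standard deviations and 36 per arm. The median Mann-Whitney P ran from 0.000004 to 0.0004 by shape. P was below 0.001 in 94% to 100% of runs and never reached 0.005. With scores rounded to whole numbers, P was below 0.001 in 88% to 100% of runs.

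**Step 5: all CHEOPS rows, by the method of step 2.**

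| Row | Group A | Group B | Printed P | P, ± as SD | P, ± as SE |
|---|---|---|---|---|---|
| Average | 3 ± 0.11 | 5 ± 0.49 | <0.005 | below 10⁻⁹ | 0.00007 |
| 30 min | 2.6 ± 0.41 | 4 ± 0.44 | <0.003 | below 10⁻⁹ | 0.02 |
| 1 h | 2.11 ± 0.98 | 4 ± 0.54 | <0.0001 | below 10⁻⁹ | 0.09 |
| 2 h | 3 ± 0.44 | 4 ± 0.65 | <0.003 | below 10⁻⁹ | 0.20 |
| 6 h | 3.05 ± 1.53 | 4.80 ± 2.04 | 0.005 | 0.00010 | 0.49 |

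Read as standard deviations, four of the five printed entries are compatible with their rows. Read as standard errors, only the average is. The 6-hour entry fits neither.

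**Step 6: ages and the faces scale.** Table 1 prints "Age (months), mean $\pm$ SD 20.68 $\pm$ 1.7 29,688 $\pm$ 3.4 0.3" (the comma is read as a decimal point). The documents give no minimum age for FPS-R, so a self-report cut-off of 36 to 48 months is an assumption. Share below the cut-off = Φ((cut-off − mean)/SD), a normal approximation:

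- ± as SD: at 36 months, about 100% of group A and Φ(6.312/3.4) = 97% of group B. At 48 months, about 100% of both.
- ± as SE, so SD = 6 × 1.7 = 10.2 and 6 × 3.4 = 20.4: at 36 months, 93% and 62%. At 48 months, 99.6% and 82%.

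The range is therefore 62% to 100%. These inputs are weak. The printed age P of 0.3 is not reproduced either (t about 14 as SD, P about 0.02 as SE). The means alone, with a 2-month minimum, would allow up to (20.68 − 2)/(36 − 2) = 55% of group A and (29.688 − 2)/(36 − 2) = 81% of group B to be 36 months or older.

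**The case against.** The strongest reply is that the headline may be correct. A reader might infer from the printed 0.005 that P<0.001 is overstated, but the documents do not support that. With ± as a standard deviation, which fits the other four rows, every CHEOPS row gives P below 0.001, and the error then lies in the 6-hour entry. The sentence may also refer only to 1 hour, where the table agrees with it. This stands, and it removes any charge of exaggeration. It does not tell the reader what was tested, nor does it remove the conflict at 6 hours.

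A reader might also infer that the single P-value covers all three scales. The abstract does not say so. It may report one scale, or the figure that is not shown.

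A third tempting reading is that the faces scale was invalid for most of these children, or biased between arms by age. The documents set no age limit for it, do not say that every child was scored on it, and show no FPS-R result. Part of the SAP text is not available, and scale assignment by age could be described there. Only the conditional point remains: if such a result is reported, the children behind it must be identified.

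Finally, choosing one scale once results are known is a post hoc choice. That is fair. CHEOPS is proposed because it is the only scale tabulated, and all its time points should stay visible.

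**Conclusion.** The point holds as a reporting inconsistency in the trial's main result. The abstract's pain claim has no stated scale or time point. The printed 6-hour CHEOPS P of 0.005 fails the abstract's bound, and it also disagrees with its own row, which gives about 0.0001 (± as standard deviation) or 0.49 (± as standard error). The recomputation assumes independent arms of 36 and a two-sided test, and it was checked against the planned rank test under five distribution shapes. Because the direction favours the caudal block throughout, the benefit on CHEOPS is not contradicted. How strong the evidence is at 6 hours depends on the unlabelled ±, and only the raw data can settle that. The documents do not establish either overstatement or unsuitability of the faces scale. This should be corrected before the pain result is relied on.

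**What to change.** 1. Recompute every Table 2 P-value from the raw data with the planned Mann-Whitney test, print exact values, and state the n analysed per arm, reconciled with the 74 in the abstract.
2. Label ± in Table 2 as standard deviation or standard error, and correct the 6-hour P or the 6-hour spread, whichever is wrong.
3. Restate the abstract result as CHEOPS at a named time point, with both group values and the recomputed P. Do not carry 0.005 forward unchecked. Say that the scale and time point were chosen after the results were known, unless a record shows otherwise, and keep all time points in the table.
4. Report FLACC as supporting evidence. If any FPS-R result is given, show it descriptively by arm, with the number and ages of the children who could be scored.

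The cost is a small reanalysis of data already collected, some rewording and at most one short table. The downside is that the headline P may become less favourable, for example if ± turns out to be a standard error or if 0.005 proves correct and the spread is wrong.

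### The parental satisfaction figures do not reconcile: 92.1% is impossible with 36 children, and Table 2's 30 (80%) and 5.0 (20%) are 83.3% and 13.9% of 36

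*Protocol*

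**What the plan says.** The Results paragraph of the Protocol abstract states: "Parental satisfaction was 92.1% in group A compared to 63.9% in group B ($P=0.012"). The Material and methods paragraph gives the number recruited: "A total of 74 patients aged two months to six years". The Conclusions paragraph says that adding the caudal block "makes it more effective, safer, and with better parental satisfaction".

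In the SAP document, under Tables and Figure legends, Table 2 is headed n=36 for each group. Its parental satisfaction rows read:

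| Level | Group A | Group B | P |
|---|---|---|---|
| Good | 30 (80%) | 5.0 (20%) | <0.002 |
| Perfect | 30 (80%) | 5.0 (20%) | <0.001 |

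The postoperative analgesia rows just above read 3.0 (8.3%) and 33 (91.7%) in group A, and 36 (100%) and 0.0 (0.0%) in group B.

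On the test, the SAP's Study population section says that "categorical variables were compared using Fisher's exact test or Pearson Chi-square test", with P below 0.05 as the threshold. The supplied text does not define a satisfied parent.

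**The concern.** The abstract and Table 2 report the same outcome with figures that cannot come from one set of 36 children per group, and the Table 2 entries are also wrong on their own terms. Better parental satisfaction is one of the stated conclusions. A reader who tries to trace it back cannot tell how large the benefit is, which answers count as satisfied, or whether 36 or 38 group A children were analysed.

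**Working it through.** **Inputs.** Abstract: 92.1%, 63.9%, P=0.012, 74 recruited. Table 2: n=36 per group, 30 (80%) and 5.0 (20%) in both satisfaction rows, and the analgesia rows. SAP, Study population: Fisher's exact or Pearson chi-square. Two-sided tests are assumed, because the sidedness is not stated.

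**1. Can the abstract's percentages be reproduced?** For n=36 the candidates are:

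- 23/36 = 63.9%, which matches group B.
- 33/36 = 91.7% and 34/36 = 94.4%. Nothing lies between them, so 92.1% cannot occur.

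A search over all pairs of group sizes totalling 74 or fewer finds one fit: 35/38 = 92.1% with 23/36 = 63.9%, and 38 + 36 = 74. No pair totals 72 or 73. Missing questionnaires in a group of 36 cannot explain 92.1%, because no denominator below 38 gives it.

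If the two extra group A children are dropped to reach 36, then depending on their answers 33, 34 or 35 remain satisfied: 91.7%, 94.4% or 97.2%. None is 92.1%.

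**2. Table 2 percentages.**

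- The analgesia rows confirm the denominator: 3/36 = 8.3%, 33/36 = 91.7%, 36/36 = 100%.
- 30/36 = 83.3%, printed as 80% (3.3 points off).
- 5/36 = 13.9%, printed as 20% (6.1 points off).
- Percentages taken across groups do not explain them: 30/35 = 85.7% and 5/35 = 14.3%.
- No whole denominator makes 30 round to 80%: 30/37 = 81.1% and 30/38 = 78.9%. The count 5 rounds to 20% only at n=25.

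**3. Levels.** As separate levels, 'Good' and 'Perfect' give group A 30 + 30 = 60 responses from 36 children. For group B the printed rows give 5 (if they are the same parents) to 10 (if separate), that is 13.9% to 27.8% of 36. The abstract implies 23. To reconcile these, 23 − 10 = 13 to 23 − 5 = 18 group B parents must sit in a level that is not printed but counts as satisfied.

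**4. The P-value.** For 35/38 against 23/36, the two-by-two table is 35, 3 / 23, 13.

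- Pearson: 74 × (35×13 − 3×23)² / (38×36×58×16) = 74 × 386² / 1,269,504 = 8.685, P = 0.0032.
- Fisher's exact: P = 0.0043.

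Neither is 0.012.

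**5. Size of the difference.**

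| Counts | Difference (points) | Newcombe 95% CI | Fisher P | Pearson P |
|---|---|---|---|---|
| 35/38 vs 23/36 | 28.2 | 9.4 to 45.3 | 0.0043 | 0.0032 |
| 33/36 vs 23/36 | 27.8 | 8.6 to 45.0 | 0.0093 | 0.0046 |
| 34/36 vs 23/36 | 30.6 | 12.0 to 47.4 | 0.0028 | 0.0014 |
| 35/36 vs 23/36 | 33.3 | 15.6 to 49.8 | 0.0006 | 0.0004 |

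The Newcombe interval combines the Wilson limits of each rate. In the first row these are 79.2% to 97.3% and 47.6% to 77.5%, so the lower limit is 28.2 − √(12.9² + 13.6²) ≈ 9.4.

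One printed row of Table 2 taken alone gives (30 − 5)/36 = 69.4 points from its counts, or 80 − 20 = 60 points from its percentages. These compare with the abstract only if no unprinted level counts as satisfied.

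**The case against.** The best defence is that the abstract agrees with itself: 35/38 and 23/36 add up to its own 74 patients. No supplied passage states 38; that figure is inferred. Two fewer children in the tables than were recruited is not an error in itself, and since part of the text was not available for this review, the explanation may exist elsewhere. All of this stands. It does not make the abstract's 92.1% compatible with a table headed 36.

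A second defence is that satisfaction was graded, with a level not shown. That could reconcile group B's 23 with the printed 5 to 10, so the group B contrast is conditional. A graded outcome could also explain the P-value. Pearson's test on some three-level splits of the same totals gives about 0.012; for example, 14, 21, 3 against 8, 15, 13 gives 0.0120. P=0.012 is therefore unverified, not shown to be wrong.

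A third is that the satisfaction rows sit in a table fragment without its own header, so not every parent need have answered. Non-response could explain 5 as 20% of 25. It cannot explain 30 as 80%, because no whole denominator gives that, and it does not explain identical entries under two levels.

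**Conclusion.** The point holds and should be fixed. Four things are wrong or irreconcilable as printed:

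- 92.1% is incompatible with n=36.
- 30 (80%) fits no whole denominator.
- 5.0 (20%) does not fit the displayed 36.
- The identical 'Good' and 'Perfect' rows cannot be separate levels in a group of 36.

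The direction is not in doubt, since both sources favour group A with P below 0.05. What is unsettled is the effect size and the group A denominator. The abstract's implied counts give 28.2 points, or 27.8 to 33.3 points once the two extra group A children are removed. The group B rate is 63.9% in the abstract against 13.9% to 27.8% in Table 2, but only if no unprinted level counts as satisfied. These figures assume that 35/38 and 23/36 are the abstract's counts and that percentages were rounded to one decimal.

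**What to change.** Re-tabulate parental satisfaction from the case report forms, counting each parent once.

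- Show every response level by group and say which levels count as satisfied.
- Give the denominator in each group and account for the 74 recruited against the 72 tabulated.
- Run one test that the SAP names, Fisher's exact or Pearson chi-square, on that table, and state which one.
- Report the difference in proportions with its 95% confidence interval.
- Put the same corrected figures in the abstract and in Table 2.

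The cost is a small re-tabulation and one re-run test on existing data. The stated rates or P-value may move in either direction.
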